2.3 Other Agents

2.3.1 Prednisone

Prednisone is a synthetic adrenocortical steroid drug with predominantly corticosteroid properties (Rayos™ package insert, 2012). Naturally occurring corticosteroids such as hydrocortisone and cortisone, which also have salt-retaining properties, are used as replacement therapy in adrenocortical deficiency states. Their synthetic analogs, such as prednisone, are primarily used for their potent anti-inflammatory effects in disorders of many organ systems. Corticosteroids, such as prednisone, cause profound and varied metabolic effects. In addition, they modify the body's immune responses to diverse stimuli. Some of these properties reproduce the physiological actions of endogenous glucocorticosteroids, but others do not necessarily reflect any of the adrenal hormones' normal functions and are seen only after administration of large therapeutic doses of the drug. The pharmacological effects of prednisone which are due to its corticosteroid properties include: promotion of gluconeogenesis; increased deposition of glycogen in the liver; inhibition of the utilization of glucose; anti-insulin activity; increased catabolism of protein; increased lipolysis; stimulation of fat synthesis and storage; increased glomerular filtration rate and resulting increase in urinary excretion of urate (creatinine excretion remains unchanged); and increased calcium excretion. Depressed production of

eosinophils and lymphocytes occurs, but erythropoiesis and production of polymorphonuclear leukocytes are stimulated. Inflammatory processes (edema, fibrin deposition, capillary dilatation, migration of leukocytes and phagocytosis) and the later stages of wound healing (capillary proliferation, deposition of collagen, cicatrization) are inhibited. For more information, see the package inserts for Rayos™ (2012) or PredniSONE™ (2012)

2.3.2 Tacrolimus

Tacrolimus, previously known as FK506, is a macrolide immunosuppressant produced by *Streptomyces tsukubaensis* (Prograf® package insert, 2018). Tacrolimus binds to an intracellular protein, FKBP-12. A complex of tacrolimus-FKBP-12, calcium, calmodulin, and calcineurin (a ubiquitous mammalian intracellular enzyme) is then formed, after which the phosphatase activity of calcineurin is inhibited. Such inhibition prevents the dephosphorylation and translocation of various factors such as the nuclear factor of activated T-cells (NF-AT), and nuclear factor kappa-light-chain enhancer of activated B-cells (NF-κB). Tacrolimus inhibits the expression and/or production of several cytokines that include interleukin (IL)-1 beta, IL-2, IL-3, IL-4, IL-5, IL-6, IL-8, IL-10, gamma interferon, tumor necrosis factor-alpha, and granulocyte macrophage colony stimulating factor (GMCF). Tacrolimus also inhibits IL-2 receptor expression and nitric oxide release, induces apoptosis and production of transforming growth factor beta that can lead to immunosuppressive activity. The net result is the inhibition of T-lymphocyte activation and proliferation as well as T-helper-cell-dependent B-cell response (*i.e.*, immunosuppression). For more information, see the Prograf® package insert.

2.4 Rationale

Activating anti-tumor immunity through blockade of the pathway mediated by the interaction between PD-1 and its primary ligands, PD-L1 and PD-L2, has demonstrated efficacy in multiple tumor types (Lipson *et al.*, 2015). However, there is a paucity of data about the safety and efficacy of anti-PD-1 in SOTRs. The same is true of agents blocking another immune checkpoint molecule, CTLA-4, such as ipilimumab. Further, little is known about the impact of combining immune checkpoint inhibitors with medications used to prevent allograft rejection on rates of tumor regression and allograft loss. These unmet needs have arisen over the last few years as clinical trials testing the above-referenced drugs have excluded SOTRs. This protocol aims to test the safety, tolerability, and efficacy of an anti-allograft-rejection regimen combined with nivolumab (anti-PD-1) +/- ipilimumab (anti-CTLA-4) in kidney transplant recipients with selected advanced cancers for whom standard anti-neoplastic treatment options would be insufficient.

The cases described in Table 1 illustrate two important concepts that underpin the current study. First, anti-PD-1 can be effective against malignancies arising in the setting of long-term immunosuppression. This efficacy signal provides a clear rationale for administration of anti-PD-1 to treat SOTRs with advanced cancer for whom standard treatment options would be insufficient. Second, the PD-1 pathway is critical in maintaining allograft tolerance in humans. It is for this reason that only patients with a transplanted kidney, generally considered a “life-enhancing” rather than “life-sustaining” organ, will be included in the proposed study.

2.5 Correlative Studies Background

Correlative studies undertaken as part of this protocol will help elucidate the biology behind allograft rejection in the setting of immune checkpoint blockade, which may affect the design of future clinical trials for recipients of life-enhancing and life-sustaining transplanted organs including lung, heart, liver, and other organs.

2.5.1 Histopathological Analyses of Allograft in Setting of Rejection

Although the histopathological characteristics of allograft rejection in the general kidney transplant population have been well described, little is known about the features of allograft rejection in SOTRs receiving immune checkpoint blockade therapy. The rationale underlying this correlative analysis is based upon the need to uncouple the anti-tumor response from the anti-allograft response brought about by administration of anti-PD-1 therapy.

In the case described above (Lipson *et al.*, 2016), anti-allograft activity was thought to be T cell-mediated. Additionally, expression of PD-L1 was detected in both the tumor and the allograft, suggesting that the immunoregulatory pathway comprised of PD-1 and its ligands is active in both microenvironments. Thus, one approach to uncoupling anti-tumor and anti-allograft immuno-activation is to find immune checkpoints that are differentially expressed in the tumor and the kidney. To identify these pathways, immunostains for an extended array of

immunoactive markers including PD-L1, PD-1, PD-L2, LAG-3, TIM-3 and others will be performed.

2.5.2 Histopathological Analyses of Tumor

In addition to the analysis described above (interrogation of the tumor microenvironment to find immune checkpoints that are differentially expressed in the tumor and the kidney allograft), we are also interested in the histological characteristics of response in immunosuppressed patients (i.e., SOTRs). Thus, H&E stained slides of tumor (pre- and on-therapy) for each subject will be reviewed. IHC will be performed for both immune checkpoint molecules (PD-L1, PD-1, LAG-3) and immune cell subsets (CD3, CD4, CD8, and CD68).

2.5.3 Circulating dd-cfDNA

In the general kidney transplant population, the dd-cfDNA assay has been shown to be predictive of Banff Grade 1B and higher active acute cellular rejection, and of antibody-mediated rejection (Bloom *et al.*, 2017). However, the assay's utility in SOTRs receiving immune checkpoint blockade therapy is unknown. We hypothesize that an early sign of allograft rejection may allow for more rapid initiation of immunosuppression and avoidance of allograft loss. We plan to compare the ability of the dd-cfDNA assay to predict allograft rejection as measured by standard clinical metrics (see Section 7.2).

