1.3 Exploratory Objective

1.3.1 To characterize correlates of the host immune response, possibly including, but not limited to:

- Histopathological characteristics of allograft rejection/loss;
- Immunological changes in the tumor microenvironment (*e.g.*, changes in T-cell subset populations or expression of immune checkpoint molecules) in paired biopsies obtained pre-treatment and on-treatment;
- Changes in donor-derived cell-free DNA (dd-cfDNA) as a marker for allograft rejection;
- Characteristics of anti-programmed death-1 (PD-1)-associated immune-mediated adverse reactions (IMARs) in this patient population treated with immunosuppression.

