7.2 Prednisone and Tacrolimus Dose Modifications for Allograft Rejection

Given the potential for rejection due to the administration of nivolumab and ipilimumab in this study, patients should be monitored closely for signs of rejection.

Markers of allograft rejection may include the following:

- Unexplained $\geq 20\%$ increase in serum creatinine over baseline,
- Development of donor-specific antigen (DSA) or non-HLA antibodies,
- Development of severe proteinuria (>1 g/day),
- Persistent increase in dd-cfDNA.

Serum creatinine (included in the comprehensive metabolic panel) will be monitored according to the schedule outlined in the treatment calendars (Section 11).

Donor-specific and non-HLA antibodies should be checked as clinically indicated at the direction of the institution's transplant nephrologist. Patients should be encouraged to report possible symptoms of rejection, including elevated temperature, elevated blood pressure, graft tenderness, and blood in the urine. Although experimental in this setting, dd-cfDNA levels (see Section 2.5.3 and the Biomarker Plan, Section 5.6) may be useful to monitor for signs of rejection.

Dipstick urinalysis should be performed per the schedule outlined in the treatment calendars. If 2+ or greater, a urine protein/creatinine ratio (spot or 24-hour) should be assessed at the direction of the institution's transplant nephrologist.

If rejection is suspected based on the above analyses, the following interventions will be triggered:

1. Hold or discontinue nivolumab (and ipilimumab, if applicable)
2. Immediately biopsy the renal allograft
 - a. If cell-mediated rejection: Increase the tacrolimus dose (target trough level = 5-10 ng/mL) and administer 500 mg IV methylprednisolone daily for 3 days, with a prednisone taper thereafter. If no improvement, administer 5 mg/kg infliximab.
 - b. If antibody-mediated rejection: Increase the tacrolimus dose (target trough level = 5-10 ng/mL), perform plasmapheresis, and administer IV immunoglobulin (Ig) per institutional protocol plus 500 mg IV methylprednisolone daily for 3 days with a prednisone taper thereafter.

A patient who experiences clinical benefit from the above regimen and still has a functional kidney allograft may restart study therapy after re-screening and consultation with the PI if the patient:

- Experienced an objective response or SD on study therapy,
- Experiences progressive or recurrent disease after having been off study therapy, and

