9.5 Analysis of Secondary Endpoints

Renal allograft rejection rate will be estimated as the proportion of subjects who experience markers of allograft rejection as defined in Section 7.2.

Allograft loss is defined as allograft rejection leading to complete, permanent, and irreversible loss-of-function of the renal allograft. All patients who receive at least one dose of nivolumab will be evaluable for allograft rejection.

Objective response rate (ORR) is defined as the proportion of subjects whose best overall response from baseline is either a CR or PR, based on RECIST 1.1 criteria. ORR will be estimated along with 95% exact CI. A minority of subjects treated with immunotherapy may derive clinical benefit and experience a delayed response, stable disease, or increased OS despite initial evidence of PD with nivolumab or combination treatment. Subjects who continue treatment beyond initial investigator-assessed, RECIST 1.1-defined progression will be considered to have investigator-assessed PD at the time of the initial progression event but may be later designated as delayed responses for purposes of determining ORR and counted as responses. The analysis of ORR will be performed on the response-evaluable population, defined as those subjects who have measurable disease at baseline, receive at least one dose of nivolumab, and undergo response assessments at ~8 and ~16 weeks. Patients who, in the opinion of the investigator, experience PD prior to 16 weeks will also be evaluable. Immune-related ORR based on immune-related response criteria (iRECIST) will also be summarized using the same method.

Among the patients who experience CR or PR, DOR is measured from the time criteria are met for CR/PR (whichever is first recorded) until the first date that recurrent disease or PD is documented. DOR will be summarized using the Kaplan-Meier method. All patients who experience CR/PR will be evaluable for DOR.

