APPENDIX D. PATIENT CLINICAL TRIAL WALLET CARD

APPENDIX E. cfDNA COLLECTION

In addition to standard clinical monitoring, this study will investigate whether the cfDNA levels can serve as an early indicator of allograft rejection in the study population. The collection is standard of care (SOC).

Streck Cell-Free DNA BCT Tubes

Streck Cell-Free DNA BCT® Tubes for dd-cfDNA should be ordered as part of the Allosure® test kit directly from the CareDx® web portal: <https://www.caredxinc.com/results-portal>. This kit includes materials for collection and shipping.

Collection of Blood in cfDNA BCT® Tubes

1. Label two 10 mL cfDNA Streck tube according to the instructions in Section 5.3.1.
2. Collect 10 mL of blood into each pre-labeled tube and gently invert to mix. **Note:** blood must be thoroughly mixed to ensure preservation of specimen.
3. **After collection, blood in cfDNA BCT tubes should never be refrigerated**, as this will compromise the specimen. Blood collected in cfDNA BCT tubes is stable at room temperature.
4. Specimens should be shipped at room temperature on the day of collection

Blood Samples for Donor Derived Cell-Free DNA

Samples should be shipped at room temperature on the day of collection via overnight delivery to CareDx®. The Allosure® collection kits will include packing instructions and shipping labels.

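### Section 7.2 counts a persistent dd-cfDNA increase among the rejection markers that dd-cfDNA is to be judged against, so the dd-cfDNA analysis and the Section 9.5 rejection rate need a reference without it

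*Combined protocol and SAP*

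**What the plan says.** Section 1.3 names as an exploratory topic "Changes in donor-derived cell-free DNA (dd-cfDNA) as a marker for allograft rejection". Appendix E puts the question as follows: "this study will investigate whether the cfDNA levels can serve as an early indicator of allograft rejection in the study population". Section 2.5.3 states that the assay's utility in transplant recipients on checkpoint blockade is unknown, and gives the planned analysis: "We plan to compare the ability of the dd-cfDNA assay to predict allograft rejection as measured by standard clinical metrics (see Section 7.2".

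Section 7.2 opens its list with "Markers of allograft rejection may include the following" and gives four items: an unexplained creatinine rise of at least 20% over baseline, new donor-specific or non-HLA antibodies, proteinuria above 1 g/day, and "Persistent increase in dd-cfDNA". Further down it adds: "Although experimental in this setting, dd-cfDNA levels (see Section 2.5.3 and the Biomarker Plan, Section 5.6) may be useful to monitor for signs of rejection".

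Section 9.5 uses the list for a secondary endpoint: "Renal allograft rejection rate will be estimated as the proportion of subjects who experience markers of allograft rejection as defined in Section 7.2". It requires no biopsy and leaves out no marker. The Biomarker Plan (Section 5.6), Section 5.7.3 and the reporting categories in Section 9.6.3 give no separate reference standard for the dd-cfDNA analysis. No section defines *persistent* or a threshold for a positive result.

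**The concern.** An accuracy study needs a reference that does not contain the test under study. Here the only pointer to a reference leads to a list that includes the test. A patient with a sustained dd-cfDNA rise and nothing else would count as a rejection because of the rise, and would then count as a correct prediction by the same rise.

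Two results are exposed. The first is the exploratory answer on dd-cfDNA. The protocol hypothesises that an early sign of rejection could help avoid graft loss, so the false-positive rate is one of the things a reader will want to know. The second is the secondary rejection rate in Section 9.5, which would include patients whose only finding is a result that Section 7.2 itself calls experimental. The primary endpoint uses allograft loss and is not directly affected.

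**Working it through.** The documents state no accuracy figure for dd-cfDNA, so there is none to reproduce. The effect can be worked out algebraically and illustrated with assumed counts.

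**Notation.** Let reference A be any rejection evidence that excludes dd-cfDNA. Against A, let TP, FN, FP and TN be the usual four cells. Let reference B be the Section 7.2 list read literally, that is, A or a persistent dd-cfDNA increase. Assume that a positive test means the Section 7.2 marker is present.

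**Algebra.** Under B, every FP patient becomes a TP patient and the other cells stay put.
- Specificity: TN/(TN+FP) becomes TN/TN = 100%.
- PPV: TP/(TP+FP) becomes (TP+FP)/(TP+FP) = 100%.
- Sensitivity: TP/(TP+FN) becomes (TP+FP)/(TP+FN+FP). The change is FP×FN / [(TP+FN)(TP+FN+FP)], which is never negative.
- NPV: TN/(TN+FN), unchanged.
- Rejection rate: (TP+FN)/N becomes (TP+FN+FP)/N.

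**Illustration.** N = 16 is the maximum in Section 9.2. The other counts are assumptions: 4 rejections under A, dd-cfDNA positive in 2 of these, and 3 of the other 12 positive on dd-cfDNA alone. So TP = 2, FN = 2, FP = 3, TN = 9.

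| Measure | Reference A | Section 7.2 list |
|---|---|---|
| Sensitivity | 2/4 = 50% | 5/7 = 71% |
| Specificity | 9/12 = 75% | 9/9 = 100% |
| PPV | 2/5 = 40% | 5/5 = 100% |
| NPV | 9/11 = 82% | 9/11 = 82% |
| Rejection rate | 4/16 = 25% | 7/16 = 44% |

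**Range.** Keep N = 16 and 4 rejections under A, but let dd-cfDNA detect 3 of them, and vary the number of dd-cfDNA-only patients.

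| dd-cfDNA-only patients | Sensitivity, A → 7.2 | Specificity, A → 7.2 | PPV, A → 7.2 | Rejection rate, A → 7.2 |
|---|---|---|---|---|
| 0 | 75% → 75% | 100% → 100% | 100% → 100% | 25% → 25% |
| 1 | 75% → 80% | 92% → 100% | 75% → 100% | 25% → 31% |
| 2 | 75% → 83% | 83% → 100% | 60% → 100% | 25% → 38% |
| 3 | 75% → 86% | 75% → 100% | 50% → 100% | 25% → 44% |

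With 9 patients (the minimum in Section 9.2), 2 rejections under A, 1 detected and 1 dd-cfDNA-only patient, sensitivity goes from 1/2 = 50% to 2/3 = 67%, specificity from 6/7 = 86% to 100%, and the rejection rate from 2/9 = 22% to 3/9 = 33%.

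**A test with no information.** Suppose the result is positive in 25% of patients whatever their status, and 25% have rejection under A. In 16 patients this gives TP = 1, FN = 3, FP = 3, TN = 9. True sensitivity is 1/4 = 25% and true specificity 9/12 = 75%. Against the Section 7.2 list they appear as 4/7 = 57% and 9/9 = 100%.

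**The case against.** The strongest reply is that Section 2.5.3 refers to *standard* clinical metrics, and dd-cfDNA is not one of them. Section 7.2 calls it experimental, Appendix E presents it as additional to standard monitoring, and the examples of kidney-related events in Section 7.1 are the other three markers. This may well be what the authors meant. The text does not settle it, though: Appendix E and the dd-cfDNA footnotes to both study calendars in Section 11 label the collection standard of care, and Section 9.5 takes the Section 7.2 list whole. Either reading could be defended, and the choice could be made after the data are seen.

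Four further points limit the concern, and they stand.
- A reader might infer that dd-cfDNA accuracy is bound to be overstated. The documents do not support that. They plan no sensitivity or specificity by name, the 100% results need a positivity rule equal to an undefined marker, and there is no bias unless at least one patient is positive on dd-cfDNA alone.
- A reader might infer that a persistent rise could never be shown to be a false positive. That also goes too far. Section 7.2 says that markers *may* include the list, suspicion leads to an allograft biopsy, and Section 9.6.3 has a category for no rejection. A negative biopsy after a dd-cfDNA signal could expose a false positive.
- Section 9.5 defines a separate secondary endpoint. Nothing says that the dd-cfDNA analysis must use the Section 9.5 count.
- The stakes are modest. The analysis is exploratory, ranked third of four in Section 5.6, in 9 to 16 patients.

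**Conclusion.** The overlap is in the text and nothing in the plan removes it. Followed literally, the plan places dd-cfDNA inside its own reference and inside the Section 9.5 rejection rate.

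The consequence is conditional. It needs at least one patient positive on dd-cfDNA alone and a positivity rule that matches the Section 7.2 marker. Under those two conditions the direction is certain, while the size depends on counts that the documents do not give. The figures above are therefore illustrations, and zero bias is among the possible outcomes. No go/no-go decision rests on this. It should still be corrected, because the question is a named objective, a secondary endpoint is touched, and the remedy is a matter of wording.

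**What to change.** Change the analysis text only; the clinical trigger list in Section 7.2 stays as it is.

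1. In Sections 2.5.3 and 5.6, state that the reference for the dd-cfDNA analysis is the allograft biopsy result where one exists, and otherwise the Section 7.2 markers other than dd-cfDNA.
2. Pre-specify what counts as a positive dd-cfDNA result, including the meaning of *persistent*. Also pre-specify which samples count: those up to the first non-dd-cfDNA evidence of rejection or, for patients with none, up to a fixed end of follow-up.
3. Report separately the patients whose work-up was triggered by dd-cfDNA alone. Note there that biopsy verification depends partly on the index test, because Section 5.4.3 ties biopsy to the Section 7.2 markers and lets patients refuse it. Note also that treatment started on a dd-cfDNA signal could prevent later evidence and make a correct early detection look like a false positive. Separate reporting shows these problems but does not remove them.
4. In Section 9.5, report the rejection rate with and without dd-cfDNA-only cases.

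The cost is a few sentences, with no new samples or procedures. The reported accuracy may look less favourable, and with 9 to 16 patients it will be imprecise under any reference.

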2.5.4 Serum and Peripheral Blood Mononuclear Cells (PBMCs)

We aim to analyze serum and PBMC to accomplish some or all of the following:

- Define new tumor antigens and their relevance to disease biology, and correlate antigen expression with immune responses and disease outcomes.
- Evaluate potential immune-related prognostic or treatment response indicators.
- Evaluate the causative mechanisms of immune-related toxicities in patients receiving cancer therapy with immune checkpoint blockade.
- Characterize factors and molecular pathways in the tumor immune microenvironment that lead to immune suppression, tolerance to tumor antigens, and cancer progression.

3. PATIENT SELECTION

3.1 Eligibility Criteria

3.1.1 Patients must be kidney transplant recipients with a functioning allograft who do not currently require dialysis.

3.1.2 Patients must have histologically or cytologically confirmed melanoma, basal cell carcinoma, Merkel cell carcinoma, cutaneous squamous cell carcinoma, or MSI-high cancers for which standard non-immunological medical, surgical, or radiation therapy would be insufficient (*i.e.*, patients who are not surgical candidates). This trial is not intended to provide therapy as a neoadjuvant approach.

3.1.3 Measurable disease as defined by RECIST 1.1 criteria, *i.e.*, at least one lesion that can be accurately measured in at least one dimension (longest diameter to be recorded for non-nodal lesions and short axis for nodal lesions) as ≥ 20 mm by chest x-ray or as ≥ 10 mm with CT scan, magnetic resonance imaging (MRI), or calipers by clinical exam is preferred, but not required. Patients with evaluable disease but no target lesions (*e.g.*, evaluable bone metastases) may be included after discussion with the Principal Investigator (PI). See Section 12 for detailed criteria.

3.1.4 Patients must have documentation, in consultation with the PI, that they received, refused, or were ineligible for the following non-immunologic therapies:

For patients with:	Prior therapies include:
BRAF-mutant melanoma	BRAF/MEK inhibitors
Merkel cell carcinoma	Platinum + VP-16
Basal cell carcinoma	Hedgehog pathway inhibitors
Cutaneous squamous cell carcinoma	Cetuximab
MSI colorectal carcinoma	FOLFOX

3.1.5 Patient's age must be ≥ 18 years. Because no dosing or AE data are currently available on the use of nivolumab and ipilimumab in kidney transplant recipients <18 years of age, children are excluded from this study, but may be eligible for future pediatric trials.

3.1.6 Patients must have ECOG performance status ≤ 2 (Karnofsky $\geq 60\%$), see Appendix A, Performance Status Criteria.

3.1.7 Patients must have normal organ and marrow function as defined below:

- leukocytes	$\geq 2,000/\text{mcL}$
- absolute neutrophil count	$\geq 1,500/\text{mcL}$
- platelets	$\geq 100,000/\text{mcL}$

- total bilirubin $\leq 1.5 \times$ institutional upper limit of normal (ULN)
- AST(SGOT)/ALT(SGPT) $\leq 2.5 \times$ institutional ULN
- serum creatinine $\leq 3 \times$ ULN

Note: patients with creatinine levels above $3 \times$ ULN may be eligible after consultation with the study PI.

